## **RISKS TO PARTICIPANTS:**

The primary risks for involvement in this study are associated with the pharmacological agent to be tested. Although cyproheptadine hydrochloride itself is not being used or administered differently than the FDA approved method, it is being used for a potentially different outcome, namely reduced unwanted muscle tone following stroke.

Some of the potential side effects of taking cyproheptadine include: diminished mental alertness, drowsiness, dizziness, hallucinations, insomnia, muscle weakness, chest congestion, headache, hypertension, increased appetite, upset stomach, diarrhea, difficulty urinating, vision problems, skin rash and dry mouth, nose, and throat, and convulsions. Although reported clinical experience has not identified differences in responses between the elderly and younger patients, elderly patients should be more cautious of possible risks. These risks may include decreased hepatic, renal or cardiac function.

To minimize these risks, we will begin with low levels of the drug and gradually titrate (increase) up to the optimal target dose for the study, which is still well within the safe level of this drug. Patients will be evaluated weekly and will be able to contact the study doctor at any time with questions or concerns. As a precautionary measure, liver profiles (requiring blood draws) will be run prior to initiation of drug administration and at the end of week 3 (chronic drug dose) to check drug impact on liver function although liver damage is not a known side effect. Following the medical screening, additional labs may be ordered at the discretion of the study doctor. Adverse events, including falls, will be assessed weekly at minimum.

Additionally, the medication may have side effects when combined with other types of drugs and/or alcohol. Some side effects of taking combined drugs may lead to confusion, high blood pressure, high fevers, tremor or muscle rigidity, and increased activity.

The effects of the study drug, cyproheptadine, on human sperm and eggs have not been studied and are therefore unknown. The effects of cyproheptadine in humans have not shown to cause negative conditions in either the mother or the fetus during pregnancy.

However, studies in animals have shown an increased risk of birth defects and fetal hormonal imbalances. The effects of this medication in women who are nursing have been shown to produce hormonal imbalances in the newborn.

Although not in the FPI for cyproheptadine, risks of falls, cognitive decline and increased mortality have been associated with use of other such drugs with antihistaminic and anticholinergic effects.

There are also risks with the use of the actuated hand orthosis, the VAEDA glove, to provide extension assistance or stretching. This device, as well as the motor used during the evaluations, has the potential to cause too much stretching, which may cause pain or damage to the joint. A number of safety features, however, have been implemented to attempt to reduce these risks, such as mechanical stops and limit switches. Additionally, the subject will be monitored continuously by research staff while using this equipment.

Skin irritation could result from the use of self-adhesive surface electrodes. This will be minimized by cleaning the skin with alcohol before and after their application. In case of any incident, emergency medical services are routinely available at the Rehabilitation Institute of Chicago and at the adjacent Northwestern Memorial Hospital emergency room.

Due to the repetitive motions of the arm and hand, subjects also risk experiencing fatigue, muscle pain, or soreness.

The electrical stimulation used to measure muscle activation can cause pain; for some people it is sharp like a prick of a needle. We will use a series of stimulation pulses that we have found to be least painful. Additionally, we will carefully adjust the stimulation level to minimize discomfort.

The cast saw used to remove the fiberglass cast placed around the wrist for the evaluations could produce burns if left for too long in one place. All study personnel will be trained in the proper use of this saw.

Some questions we ask from the BDI-II examination may be upsetting or make the subject feel uncomfortable. If they do not wish to answer a question, they may skip it and go to the next question. A BDI-II total score above 13 will be reported to the study doctor immediately, and a private consultation with the study doctor arranged. Likewise, any suicidal ideations revealed through the BDI, regardless of total score, will be reported to the study doctor. In either case, the individual will be advised to seek counseling.

### POTENTIAL BENEFITS TO PARTICIPANTS:

Although it has been shown that some benefit may be derived from taking cyproheptadine or from performing repetitive motion tasks or stretching, subjects are not guaranteed any direct benefit from participating in this research study. Participation in this study may aid in our understanding of the nature of movement impairment after stroke and may eventually improve rehabilitation of upper extremity function.

## VULNERABLE POPULATIONS: N/A

### COMMUNITY-BASED PARTICIPATORY RESEARCH: N/A

### SHARING OF RESULTS WITH PARTICIPANTS:

IRB #: STU00078099 Approved by NU IRB for use on or after 6/23/2020 through 6/22/2021.

PROTOCOL TITLE:

This study is registered on clinicaltrials.gov NCT02418949. Therefore, study results for the outcome measures will be available at the completion of the study. Individual laboratory test results will not be shared with participants unless deemed necessary by the study doctor nor will they be available on clinicaltrials.gov.

### SETTING:

All training, hand evaluation sessions will be held in the Arms and Hands Lab (22 floor) of the Shirley Ryan AbilityLab, [name]. This is also where subjects will be given their allotment of pills for each change in dosage and see the study doctor for examinations. Research staff will escort subjects to the outpatient lab for blood draw at baseline and the end of week 3 (before beginning therapy treatment) to monitor the drugs effect on your liver function.

## **RESOURCES AVAILABLE:**

The Shirley Ryan AbilityLab will provide all space and resources required for the completion of the proposed study, including areas to conduct subject assessments and experiments, offices for the Principal Investigator, [name], and the other project personnel, and administrative and information system support. Specifically, the proposed study will be conducted in the Arms and Hands Lab of the Shirley Ryan AbilityLab, which contains 17 laboratories devoted to the study of human sensorimotor integration and control.

The RIC is a 182-bed specialty hospital in the downtown Chicago area with full accreditation by the Joint Commission on Accreditation of Healthcare Organizations and the Commission on Accreditation of Rehabilitation Facilities. The RIC brings together high quality comprehensive care for individuals with disability, research into the mechanisms and management of disabling conditions, and training of professionals and the public about disability and approaches to its management. It provides acute inpatient rehabilitation, day rehabilitation, outpatient clinics, and home health for stroke, spinal cord injury, traumatic brain injury, and orthopedic patients. The RIC is an academic affiliate of the Northwestern University Feinberg School of Medicine and is the home of its Department of Physical Medicine and Rehabilitation.

Stroke survivors who are willing to participate in the proposed study will be drawn from the outpatient facility of the Shriley Ryan AbilityLab. In addition, the Sensory Motor Performace Program (SMPP) maintains an Institutional Review Board (IRB) approved Clinical Neuroscience Research Registry of over 900 stroke survivors who wish to be contacted for possible participation in research studies.

Shirley Ryan AbilityLab has its own pharmacy. Cyproheptadine and placebo will be dispensed from this pharmacy.

Shriely Ryan AbilityLab is highly supportive of research and is striving to further integrate research and clinical care. Therapists working in SMPP typically split their time between SMPP and the clinic. RIC currently hosts a number of federally funded centers, including the Rehabilitation Research and Training Center for Stroke, sponsored by the National Institute on Disability and Rehabilitation Research. [name] is the PI and Director for this Center. Additionally, RIC is constructing a replacement facility to open in 2017, two blocks from its current site. The concept for the new facility is to infuse biomedical science and research into the clinical environment. Thus, research laboratories will sit adjacent to clinical therapy space and a culture of interaction and cooperation will be fostered. As a model, in the current facility RIC opened the Patient Recovery Unit in which patients receive intensive, customized therapy guided by the latest research findings.

### PRIOR APPROVALS: N/A

### **RECRUITMENT METHODS:**

Recruitment for potential participants will be done through the IRB approved research registry. Flyers will be placed in Shirley Ryan AbilityLab, clinics, and the Life Center and on the clinical trials webpage for the Shirley Ryan AbilityLab Referrals from the study doctor or other colleagues will also be screened.

Following the initial screening with the research staff, further participation will require passing a medical examination with the study doctor as well as completing a clinical assessment for randomization purposes prior to study enrollment. The stipend is \$20 for this visit.

During the study, the stipend for each treatment session is \$20 and the stipend for each evaluation session is \$40. These funds are provided to help support time and travel associated with participation. If a session needs to be repeated at the behest of the study doctor, PI, or due to researcher conflicts and/or equipment malfunction the stipend will be duplicated.

RIC is moving away from using petty cash. During this transition period you may be paid in cash or by ClinCard. If a ClinCard is available when you enter into the study, you will be paid by card. If a ClinCard is not available, then you will receive cash payments on the day of your research visit.

## NUMBER OF LOCAL PARTICIPANTS:

We are targeting 100 subjects to complete the study.

This would break down into four groups of 25:

- Cyproheptadine and Active Hand Therapy
- Placebo and Active Hand Therapy
- Cyproheptadine and Passive Stretching
- Placebo and Passive Stretching

We estimate needing to enroll 200 subjects in order to reach our target due to participants not meeting inclusionary/exclusionary criteria or to dropping out of the study.

### CONFIDENTIALITY: N/A

### **PROVISIONS TO PROTECT THE PRIVACY INTERESTS OF PARTICIPANTS:**

A private room may be provided to the subject during administration of the side effects checklist, medical examinations, or other surveys, such as BDI-II, where sensitive information is discussed. As always, the subjects have the right to refuse to answer any questions which may make them feel uncomfortable.

The study doctor may access medical records or sensitive information for recruiting purposes.

### COMPENSATION FOR RESEARCH-RELATED INJURY:

If a subject becomes ill or gets an injury or illness as a result of study medications or procedures, you should seek medical treatment through your doctor or treatment center of choice. You should promptly tell the study doctor about any illness or injury.

The hospital will not pay for medical care required due to an injury or illness as a result of their participation in this research study. However, this does not keep them from seeking to be paid back for care required because of a bad outcome. Subjects are welcome to seek medical treatment through their doctor or treatment center of choice.

## **ECONOMIC BURDEN TO PARTICIPANTS:**

There will be no costs to participants for being in this study. The cost of the drug, the therapies and the lab work tests will be covered by the study.

## **CONSENT PROCESS:**

This study will obtain written informed consent from all study participants. The consenting process will take place at Shirley Ryan AbilityLab, [name] with an approved member of the study team. A full discussion about the study will take place before the medical examination; research staff will be available to answer any questions. Subjects will be given ample time to meet with family or friends to discuss details of the study prior to giving consent. For documentation of the consent process, a participant's signature may be obtained electronically.

## Adults Unable to Consent

The individuals from whom permission will be obtained in order of priority: durable power of attorney for health care, court appointed guardian for health care decisions, spouse, and adult child.

## PROCESS TO DOCUMENT CONSENT IN WRITING:

Informed consent will be documented in writing through our Consent and HIPAA Authorization for Research form and uploaded to the Nitro Study Tracker.

### DRUGS OR DEVICES:

The drugs used in this study will be administered by the Shirley Ryan AbilityLab pharmacy for each subject. A study team member will deliver the prescription to the participant during a scheduled visit. If there is any time the drug will be in the lab prior to this delivery, it will be temporarily locked in a designated cabinet approved by the pharmacy.

Title: Altering Activation Patterns Post-stroke **NCT:** NCT02418949 **Date:** 6/4/2014

Analysis: Spasticity will be quantified using the MCP angular position and torque data from the trials of imposed MCP rotation [27, 66-68]. Namely, the nominally passive torque curve (recorded during the 10°/s trial) will be subtracted from the total torque curve (recorded during the 300°/s). Mean reflex torque will then be computed from the resulting signal by averaging across a 300-ms period beginning at the end of stretch. The EMG data, normalized by the values recorded during maximum contraction, will be used to confirm that a reflex occurred. The FDS signal must surpass a threshold of 5% of maximal contraction for classification as a spastic stretch reflex and subsequent evaluation. Coactivation during voluntary tasks will be computed from the ratio of normalized EDC/FDS for flexion and FDS/EDC for extension. Values closer to 0 indicate less coactivation. Relaxation time will be estimated as the elapsed time from cessation of the auditory tone to the FDS signal dropping below a threshold level equal to three standard deviations of the resting signal [34]. Active isometric flexion and extension torque will be found by subtracting the initial, passive torque from the peak torque recorded during the respective trials.

Statistical analyses will be employed to assess the effect of cyproheptadine on these outcome measures. We will perform repeated measures analysis of variance (rmANOVA) with the between-subject factor Drug (cyproheptadine, placebo) and the within-subject factor evaluation Session (pre-administration, week 1, week 2, week 3 - see Fig. 1). To test the first hypothesis, addressing efficacy in reducing hyperexcitability, the measures spastic reflex, FDS relaxation time, and coactivation ratio will be used as dependent variables in a MANOVA. Should evidence of a significant effect appear, i.e., a Wilk's lambda value < 0.05, we will perform subsequent post-hoc ANOVAs to test the effects on individual dependent variables. To examine the second hypothesis, regarding loss of strength, separate rmANOVAs will be conducted for extension and flexion strength. Similarly, as we wish to minimize Type II errors for these potentially negative outcomes, separate rmANOVAs will be run for ESS and BDI-II without correction. Normality of the residuals will be tested for these parametric tests and non-parametric tests will be run if normality assumptions are violated.

We will have 50 subjects in each of our Drug groups (cyproheptadine/placebo) in accordance with the power analysis performed for the whole study (see *Aim 2: Analysis*). Thus, we will be able to detect an effect size of 0.22 with a power of 80% for an α of 0.05 (G*Power 3.0 software [69]). In our pilot study examining a single dose of cyproheptadine, we observed a much greater effect size of 0.60 for the reduction in relaxation time. Importantly, the targeted subject numbers will allow us to detect even moderate decreases in strength or increases in somnolence.

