### PRINCIPAL INVESTIGATOR: [name] Shirley Ryan AbilityLab [name] [contact]

#### **VERSION NUMBER: 7**

#### VERSION DATE: January 8, 2019

#### **OBJECTIVES:**

Aim 1: Determine the capability of an anti-serotonergic agent to reduce hyperexcitability poststroke without compromising voluntary strength.

Aim 2: Assess the efficacy of using a multimodal intervention combining an antimonoaminergicagent with upper extremity training.

Hypothesis: We investigators hypothesize that the group receiving the combined cyproheptadine and active movement therapy will have better outcomes than the groups receiving passive therapy or placebo.

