#### BACKGROUD:

Chronic sensorimotor impairment of the upper extremity is prevalent in more than 6 million stroke survivors in the U.S. (Go, et al., 2013), especially in the distal upper extremity (Trombly, 1989). In our studies of the impairment mechanisms of hand motor control after stroke, e.g., (Cruz, et al., 2005; Kamper, et al., 2006; Triandafilou, et al., 2011), we have been struck by two phenomena which arise following the original brain lesion; i) involuntary hyperexcitability of the motor units in certain muscles and ii) the difficulty in producing and controlling voluntary muscle activation. We propose to directly treat both of these phenomena simultaneously in order to improve motor control of the hand and arm. We will reduce motoneuronal hyperexcitability through administration of an anti-serotonergic drug which does not increase weakness, and we will guide the generation of proper muscle activation with a custom device and computer program. We believe that our multimodality treatment approach is innovative in that we combine the use of pharmacological agents with individualized movement therapy in a manner that can be used with patients with poor initial motor control. In separate preliminary studies, we were able to show that a single dose of the agent cyproheptadine could reduce unwanted muscle excitation without decreasing voluntary strength (Seo, et al., 2011) and that active motor training, assisted by an electromyographically (EMG) controlled actuated glove, could lead to statistically significant improvement both in measures of impairment and task performance. In this study, we will combine these approaches to create a novel treatment paradigm for improving motor control of the distal upper extremity after stroke. These techniques are amenable to rapid and widespread integration into the clinic for the arm and hand, and could be applied to the lower extremity as well.

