### Outcome Measures:

Subjects will be tested at the Arms and Hands Lab at baseline and the end of each week during the titration phase. Thus, data will be collected prior to administration of any agent, after one week at the lowest dosage of up to 8 mg per day, after one week at the next dosage of up to 16 mg per day, and after one week at the highest dosage of up to 24 mg per day. Data from the 4 testing sessions will be used to assess the impact of cyproheptadine on stroke. All outcome measures will be collected during each testing session. Pill counts will be performed each week as well to gauge subject compliance.

**Fig. 6.** Depiction of the interface between the fingers and the device. The motor shaft rotates the U-piece coupled to the proximal phalanges of the fingers. For the spasticity experiments, the proximal and distal interphalangeal joints will be fixed in neutral with finger splints.

Three potential manifestations of motoneuronal hyperexcitability will be quantified: spasticity, excessive coactivation during voluntary contraction, and prolonged muscle relaxation time. Spasticity will be precisely measured using techniques we have successfully employed in the past in which all four fingers are coupled to a servomotor through a custom jig (Fig. 6). Rotation of the servomotor shaft produces equivalent rotation of the MCP joints. The servomotor will impose constantvelocity rotation of the MCP joints in order to stretch the long finger flexors. Fast MCP rotation (300°/s) will be applied to evoke a stretch reflex. Slow MCP rotation (10°/s) will be imposed to measure nominally passive resistance. Wrist orientation and position will be fixed with a fiberglass cast which is subsequently clamped to a table (Fig. 6). MCP angle, angular velocity, and torque are recorded for analysis of spasticity. EMG recordings will be obtained with surface

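### The 5% FDS rule for evaluating a stretch reflex is not limited to the pre-drug session and leaves sub-threshold stretches undefined, so the Aim 1 spasticity estimate can depend on the on-treatment response being tested

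*SAP*

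**What the plan says.** Protocol, Objectives, Aim 1: "Determine the capability of an anti-serotonergic agent to reduce hyperexcitability poststroke without compromising voluntary strength". Spasticity is one of the hyperexcitability measures. The SAP (Analysis) defines it as mean reflex torque: the torque curve at 10°/s is subtracted from the curve at 300°/s, and the result is averaged over 300 ms from the end of stretch.

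The SAP then adds an EMG check. On its purpose: "The EMG data, normalized by the values recorded during maximum contraction, will be used to confirm that a reflex occurred". On the rule: "The FDS signal must surpass a threshold of 5% of maximal contraction for classification as a spastic stretch reflex and subsequent evaluation".

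The measure feeds the test of the first hypothesis, where "the measures spastic reflex, FDS relaxation time, and coactivation ratio will be used as dependent variables in a MANOVA". The analysis has "the within-subject factor evaluation Session (pre-administration, week 1, week 2, week 3"). The protocol (Outcome Measures) agrees: "Data from the 4 testing sessions will be used to assess the impact of cyproheptadine on stroke". On numbers, the SAP says: "We will have 50 subjects in each of our Drug groups".

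Neither document ties the 5% rule to a session. Neither says whether a sub-threshold stretch is zero, missing, or a reason to drop the trial, session or subject. Entry requires hand Stage 2 or 3 but no minimum reflex.

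**The concern.** The rule decides which reflexes are evaluated from the size of the reflex itself, and at weeks 1-3 that size is a post-randomisation outcome. If cyproheptadine suppresses the reflex, more drug-arm stretches fall below 5%. Under a literal reading the drug subjects who remain are those who began with larger reflexes or responded less, so the randomised comparison is lost for this measure.

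There may be a knock-on effect, which is inference and not stated in the SAP. A complete-case MANOVA would drop a subject with no reflex value altogether, losing that subject's relaxation-time and coactivation data as well.

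At stake are the estimate and power for one Aim 1 mechanistic outcome. The protocol's Study Endpoints name GWMFT completion time as primary and grip relaxation time as secondary. The 5% rule defines neither.

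**Working it through.** **1. The plan's own figure.** The SAP states a detectable effect size of 0.22 at 80% power and α 0.05. Take 0.22 as Cohen's f for the Drug factor, with N = 100, m = 4 sessions and within-subject correlation ρ = 0.5. The reading as f and the value of ρ are assumptions. Then λ = f²·N·m / (1 + (m−1)ρ) = 0.0484 × 400 / 2.5 = 7.74 on 1 and 98 df. Power is 78.7% and the detectable f is 0.224, so the figure reproduces. It requires all 100 subjects to contribute: the same f gives 69% power at N = 80 and 56% at N = 60.

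**2. Illustrative model (all values assumed).** Reflex EMG is log-normal with median M = 10% of maximum, log-SD 0.8 and between-session correlation 0.7. Torque is proportional to EMG. The true reduction is 30% at weeks 1-3, or ramps through 10%, 20% and 30%. There are 400,000 simulated subjects per arm.

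**3. Closed-form checks at one session.** The evaluable share is Φ(ln(M/5)/0.8).
- Placebo, or either arm at baseline: Φ(ln 2/0.8) = Φ(0.866) = 81%.
- Drug at week 3 (median 7): Φ(ln 1.4/0.8) = Φ(0.421) = 66%.

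With zero-scoring, the share of mean torque kept is Φ(0.8 + ln(M/5)/0.8), which is 0.952 for placebo and 0.889 for drug.
- Apparent week-3 reduction: 1 − 0.7 × 0.889/0.952 = 35%.
- Raw change relative to the ungated effect: (0.952 − 0.7 × 0.889)/0.3 = 1.10.

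**4. Simulated results at median 10%.** Where two values are given, they span the constant and ramped effects.

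| Handling | Kept, placebo v drug | Week-3 reduction (true 30%) | Raw change ÷ ungated |
|---|---|---|---|
| Complete cases | 63% v 47-52% | 19-22% | 1.35-1.42 |
| Sub-threshold session lost, change paired within subject | 81% v 66% of week-3 sessions | 20% | 1.22 |
| Sub-threshold scored zero | all | about 35% | 1.10 |
| Rule at pre-administration only | 81% v 81% | 30% | 1.14 |

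The 20% in the second row uses all evaluable week-3 sessions. Under complete cases, retained drug subjects start with a mean reflex 8-13% higher than retained placebo subjects, and the four-session Drug main effect is 0.63-0.66 of its ungated size.

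**5. Separating selection from population.** Under a proportional effect, any gate that keeps larger reflexes raises raw change, and the baseline-only gate already gives 1.14. Relative to baseline-qualified subjects, complete cases give about 1.18-1.24 and paired session loss 1.22/1.14 = 1.07. Only this remainder comes from on-treatment selection.

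**6. Sensitivity.** Complete cases at median 20%: week 3 appears as about 26% and raw change is 1.11-1.14. At 40%: retention is 99% v 96-97%, week 3 appears as 29%, raw change is 1.02-1.03 and the main effect is 0.95. A second model used median 9% and log-SD 0.5, and gated at baseline and week 3. Relative to baseline-qualified subjects, raw change was 1.13-1.30 for a uniform proportional response, 1.00 for a constant additive one and 0.79-0.91 where response varied between subjects.

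**7. Power and the null.** With 50 per arm and a t test on raw change (not the SAP's MANOVA), power at median 10% is 52-54% ungated and 36-38% complete-case. At 40% there is no loss. Rejection under the null is 4-5%. That null assumes the drug leaves maximal EMG unchanged. If the drug multiplied the maximum by 0.8 or 1.25, the effective threshold would be 4 or 6.25. The evaluable week-3 share would then be Φ(ln 2.5/0.8) = 87% or Φ(ln 1.6/0.8) = 72%, against 81% on placebo, with no reflex effect at all.

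**The case against.** The strongest reply is that the 5% rule is a detection criterion. The sentence before it says the EMG serves to confirm a reflex, so a stretch without confirmation could simply count as no reflex torque. The rule could also act trial by trial, without losing a session. Both readings are fair, and the text does not choose between them. Zero-scoring removes the exclusion but still inflates the effect, so the gap matters either way.

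The size is also assumed throughout. The protocol's Background cites "the difficulty in producing and controlling voluntary muscle activation", so the normalising maximum may be low and normalised reflexes well above 5%, in which case little is lost. That stands. It also stands that the check guards against non-reflex resistance, and that the supplied SAP points to an Aim 2 analysis text that was not supplied and may cover missing data.

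Four stronger readings are tempting and are not supported:
- *Raw change reverses direction between complete-case and session-only handling.* It appears to do so (0.80-0.81) only if unpaired session means are subtracted. The SAP's Session factor is within-subject, and paired change gives 1.22, the same direction as complete cases.
- *The whole 1.35-1.42 is selection on treatment.* Part of it is the change of population shown in step 5.
- *The test is invalid under the null.* There is no type I error inflation if the drug affects neither the reflex nor the maximal EMG.
- *The trial's main result is at risk.* The rule defines neither listed endpoint.

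**Conclusion.** The concern holds in a limited form. As worded, the rule lets evaluation at weeks 1-3 depend on the response under test, and it leaves open a choice that changes the answer. Under the illustrative median of 10%, complete cases understate the week-3 between-arm reduction (19-22% against 30%) and overstate raw change (about 1.18-1.24 times the effect in baseline-qualified subjects). In that model the direction depends on whether levels or changes are compared. If response varies between subjects, change can be understated too. Zero-scoring overstates both, modestly. At a median of 40% the effect is negligible for raw change and for the week-3 level. The wording gap is certain. The size is not, because the documents give no reflex distribution, sub-threshold rate or expected drug effect on the reflex. It should be fixed because it is cheap to fix before unblinding, but it bears on an Aim 1 mechanistic outcome only.

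**What to change.** State in the SAP that mean reflex torque (300°/s minus 10°/s) is computed and analysed for every subject at every session, whatever the FDS amplitude. Keep the 5% rule as a descriptive flag and report the proportion above it by arm and session. Use zero-scoring only as a sensitivity analysis. Say how a subject missing one of the three MANOVA variables is handled.

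If an EMG-confirmed set is wanted, apply the 5% rule at the pre-administration session only, so that selection cannot depend on treatment. The result then applies to subjects with a baseline reflex.

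The change is to wording, since the torque is recorded anyway. Analysing all sessions adds some noise and may admit non-reflex torque. The baseline gate avoids much of that but loses about 19% of subjects at median 10% (28% at 8%, 4% at 20%), leaving roughly 50 × 0.81 = 40 per Drug group at median 10%.

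### The SAP makes no provision for non-sphericity in its four-session rmANOVA; an uncorrected 5% Drug x Session test would run at about 5.8%-7.3% if session correlations decay over time

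*SAP*

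**What the plan says.** The Analysis section of the SAP sets the model for the drug comparison during titration: "We will perform repeated measures analysis of variance (rmANOVA) with the between-subject factor Drug (cyproheptadine, placebo) and the within-subject factor evaluation Session". The levels of Session are "pre-administration, week 1, week 2, week 3 - see Fig. 1". The protocol, under Outcome Measures, ties these visits to the rising dose: the first is before any agent, the second is "after one week at the lowest dosage of up to 8 mg per day", and the other two follow a week at each higher level.

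Three uses of the model are described.

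- For the first hypothesis, "the measures spastic reflex, FDS relaxation time, and coactivation ratio will be used as dependent variables in a MANOVA". ANOVAs on the single measures follow only if that test is significant.
- Flexion and extension strength each get their own rmANOVA.
- ESS and BDI-II are treated likewise. There the stated aim is to keep Type II error low, because they are possible harms.

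The one assumption check is this: "Normality of the residuals will be tested for these parametric tests and non-parametric tests will be run if normality assumptions are violated". The SAP does not mention sphericity, an epsilon correction, a multivariate test across sessions or an unstructured covariance. It also does not say which term of the model decides each hypothesis.

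On size and power it says: "We will have 50 subjects in each of our Drug groups (cyproheptadine/placebo") and "we will be able to detect an effect size of 0.22 with a power of 80% for an α of 0.05".

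**The concern.** With two repeated measures sphericity holds automatically; with four it does not. The univariate F-test for Session and for Drug x Session is exact only when all differences between pairs of sessions have the same variance. At weekly visits, neighbouring sessions are usually more alike than distant ones. That alone breaks the condition, and it can do so when the drug has no effect.

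The interaction is the natural place to look for a drug effect here. The first session precedes dosing, so an effect of titration appears as a group difference in change across sessions, whereas the Drug main effect averages in an untreated visit.

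Two things are at stake. One is a mildly liberal test on titration-phase outcomes. These include grip relaxation time, which the protocol's Study Endpoints section lists as the secondary outcome. The other is an unsettled choice: uncorrected, corrected and multivariate p-values can fall on different sides of 0.05, and the SAP does not say which one counts.

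**Working it through.** **Inputs from the SAP.** Two drug groups of 50 (N = 100), m = 4 sessions, alpha 0.05. Interaction df are (2-1)(4-1) = 3 and (100-2)(4-1) = 294.

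**Inputs assumed.** The correlation and SD pattern across sessions, equal covariance in both groups, normal errors and complete data. None of the covariance values is in the documents.

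**1. The plan's own figure.** Read 0.22 as Cohen's f for the between-subject Drug effect, with an assumed within-subject correlation rho = 0.5. The noncentrality is

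lambda = f² N m / (1 + (m-1) rho) = 0.0484 x 400 / 2.5 = 7.744, on 1 and 98 df.

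Power is 78.7%, and the f detectable at 80% power is 0.224, so 0.22 is reproduced to rounding. With the same rho, the Drug x Session interaction under sphericity would give a detectable f of 0.118. The stated figure therefore fits the Drug main effect, which does not depend on sphericity.

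**2. Size of the uncorrected interaction test.** Let l1, l2, l3 be the eigenvalues of the covariance of three orthonormal session contrasts. Then

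epsilon = (l1 + l2 + l3)² / [3 (l1² + l2² + l3²)],

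which runs from 1 (sphericity) down to 1/3. The Box approximation to the true size is P[F(3 epsilon, 294 epsilon) > c], where c is the 95% point of F(3, 294). Simulation of the exact weighted chi-square ratio (1,000,000 draws) checks it.

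| epsilon | Box | Simulated |
|---|---|---|
| 1.00 | 5.0% | 5.0% |
| 0.90 | 5.6% | 5.5%-5.6% |
| 0.80 | 6.3% | 6.0%-6.3% |
| 0.70 | 7.1% | 6.7%-7.1% |
| 0.60 | 8.0% | 7.5% |
| 1/3 | 10.8% | 10.7% |

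**3. Plausible patterns.** AR(1) correlation of 0.5 gives epsilon 0.86 and size 5.8%; 0.8 gives epsilon 0.72 and size 6.6%. Full data sets (20,000 null trials of 50 v 50 per case) gave:

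- AR(1) 0.5-0.9, constant SD: 5.8%-6.7%
- the same, with the SD growing to 1.5 times over the sessions: 6.1%-7.3%
- the same cases with Greenhouse-Geisser degrees of freedom: 4.7%-5.0%

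The simulation standard error is about sqrt(0.06 x 0.94 / 20,000) = 0.17 points, so each end of these ranges is good to roughly 0.3 points.

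**4. Checks on scope.** In four covariance patterns, a multivariate (Hotelling) test of Drug x Session ran at 4.8%-5.2%, and the Drug main effect at 4.8%-5.1%.

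**5. Price of correcting.** The approximate detectable interaction f (rho = 0.5) rises from 0.118 at epsilon 1 to 0.122 at 0.9, 0.133 at 0.7 and 0.141 at 0.6. In simulations with a drug effect, Greenhouse-Geisser lowered nominal power by about 2-7 points. In one case with a linear drug trend, AR(1) 0.9 and growing SD, it went from 84.7% to 80.2%. Part of that loss is power that the uncorrected test gains only by exceeding 5%.

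**The case against.** The best case for the plan is that it is silent rather than wrong, and that the effect is small and confined. Much of this stands.

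- A reader might infer that the SAP plans to leave sphericity uncorrected, because it says that the ESS and BDI-II analyses are run with no correction. In context that remark concerns multiplicity. The documents show only that nothing is provided.
- A reader might infer that the test is known to exceed 5%. It is not: under compound symmetry it holds 5.0%, and no covariance is given.
- A reader might argue that the rising dose must make later sessions more variable. Under the null the drug does nothing, so dose cannot spread the outcomes, and the placebo group gets no active dose. Growth in SD is an assumption; decaying correlation is the firmer reason.
- A reader might extend the point to every Aim 1 conclusion. The three hyperexcitability measures pass through a MANOVA first. How Session enters it is not stated, so whether the gate depends on sphericity cannot be determined. If one measure truly responds, however, the gate opens and the others go to follow-up ANOVAs with no correction named.
- The Drug main effect is unaffected, and the SAP never names Drug x Session as decisive.
- For strength, ESS and BDI-II a slightly liberal test errs towards signalling harm, which matches the SAP's stated priority for ESS and BDI-II.
- The protocol's primary outcome, GWMFT completion time, is not among the measures in this analysis.

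These points limit the concern without removing it. The named method, run with only the checks that the SAP lists, is liberal under ordinary serial correlation.

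**Conclusion.** The concern holds in conditional form. If the uncorrected F-test is used and session correlations decay as AR(1) 0.5-0.9, the nominal 5% Drug x Session test runs at about 5.8%-7.3%, an excess of 0.8 to 2.3 points. The limits over all covariances are 5.0% and about 10.8%. The figures assume normal errors, complete data and the same covariance in both groups.

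The tests exposed are the within-subject terms of the rmANOVAs for flexion and extension strength, ESS and BDI-II. The follow-up ANOVAs for reflex, relaxation time and coactivation are exposed if they include Session. The Drug main effect, and with it the most likely basis of the 0.22 power statement, is not.

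This is a modest defect that should be corrected because the correction is cheap. It does not invalidate Aim 1.

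**What to change.** Add one of the following to the Analysis section of the SAP.

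- **Corrected rmANOVA.** State that all tests of Session and Drug x Session, including the ANOVAs that follow the MANOVA, use Greenhouse-Geisser-corrected degrees of freedom, and that only those p-values count. The cost is one sentence and about 2-7 points of nominal interaction power in the cases simulated. Some of that loss falls on the harm outcomes, where the SAP wants to limit Type II error, so it should be accepted knowingly.
- **Mixed model.** Replace the rmANOVA by a model with the same Drug x Session means, unstructured covariance across the four sessions (4 x 5 / 2 = 10 parameters, manageable with 100 subjects) and Kenward-Roger degrees of freedom. This needs no sphericity and keeps subjects who miss a session. That is useful because the protocol, under Number of Local Participants, expects to enrol 200 to obtain 100 completers and gives dropout as one of the reasons. The cost is rewriting a few lines of the SAP.

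Either way, the SAP should also name the term that decides each hypothesis and state how Session enters the MANOVA. No change to visits, data collection or sample size is needed.
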